2.3 Part 2 Schedule Escalation Segment

Once the MTD for patients receiving TK216 by continuous infusion for seven days has been identified, the tolerability of longer infusion times will be determined.

This segment will also be performed in sequential cohorts of patients receiving TK216 intravenously by continuous infusion via a central venous catheter. A "3+3" patient enrollment scheme will be followed during the schedule escalation. If 2 of 3 patients experience a first-cycle DLT then accrual to the cohort will cease, and the subsequent cohort will receive TK216 at the next lower dose. If a first-cycle DLT is seen in one of the 3 patients in a cohort, that cohort will enroll an additional 3 patients. DLT is defined as an adverse event occurring during the first cycle that is at least possibly related to TK216 and meets the DLT definition for the schedule escalation segment (Table 2). When 0 of 3, or 1 of 6 patients in a cohort experience first cycle DLT, the dose will be escalated in the subsequent cohort.

The starting daily dose level in the schedule escalation segment will be the MTD determined in the Part 1 dose escalation segment as described in the previous section.

The first schedule escalation cohort will receive TK216 by continuous IV infusion for 10 days.

The selection of dose and schedule for subsequent cohorts will be made by the Investigators and Sponsor after evaluating the first cycle results of the previous cohort. The dose level for newly enrolled patients will be assigned by Oncternal Therapeutics, Inc. at the time of registration.

By way of illustration:

- If 0 of 3 or 1 of 6 patients in the first dose escalation experience first cycle DLT, the second schedule escalation cohort will receive TK216 by continuous IV infusion at the same dose for 14 days.
- If 2 or more patients in the first dose escalation experience first cycle DLT, the second schedule escalation cohort will receive TK216 by continuous IV infusion at the next lower dose for 10 days.

The same decision algorithm will be used to select the dose and schedule for the third and subsequent schedule escalation cohorts.

It is anticipated that 4 to 6 cohorts will be completed during the schedule escalation segment of this trial. With the concurrence of the investigators and the study sponsor, further testing may be performed in up to 12 additional patients per dose level to refine the estimation of the MTD and RP2D at intermediate dose levels or to define a higher MTD and RP2D while using Cycle 1 primary supportive care prophylaxis (e.g., with growth factors, antidiarrheals, antiemetics) for bone marrow and/or gastrointestinal toxicities.

The duration of cycles will be variable. Following the scheduled infusions of TK216, a rest period will begin. The next cycle for a patient may begin as soon as all the patient's toxicities attributed to TK216 have resolved to less than Grade 3, or are clinically tolerable Grade 3 toxicities.

Once a patient completes Cycle 2 of any schedule escalation cohort, vincristine can be administered on Day 1 of a subsequent cycle and on Day 1 of each subsequent cycle. The initial dose of vincristine on Day 1 of the starting cycle will be 0.75 mg/m² given via intravenous infusion prior to the initiation of the TK216 infusion. Subsequent doses beginning on Day 1 of the next cycle and beyond will be 1.5 mg/m² up to a maximum dose of 2 mg.

Additional cycles of therapy may be administered provided that the patient meets the following criteria on Day 1 of each cycle:

- ANC \geq 1,000/mm³
- Hemoglobin \geq 8.0 gm/dL (Blood transfusions are permitted.)
- Platelets \geq 50,000/mm³
- Non-hematologic toxicity(s) recovered to less than Grade 3, or are clinically tolerable Grade 3 toxicities
- In patients receiving vincristine, clinically tolerable neurotoxicity, and lack of seizure activity

A rest period of 14 days is required following the first cycle, but the rest period may be reduced following subsequent treatments if the above criteria are met.

If TK216 treatment has been well tolerated in Cycle 1 and 2, starting in Cycle 3 the duration of the TK216 infusion may be increased (e.g. from 14 to 17 or 14 to 21 days). If the longer infusion is well tolerated, the duration of the TK216 infusion may be increased further in subsequent cycles. There is no maximum treatment duration. If a longer infusion time is not well tolerated, the patient may remain on study, but receive a shorter duration of TK216 infusion in the next treatment cycle. The assessments noted for Days 8+/-1 and 15+/-1 in the Section 16.3 Schedule of Events (Schedule Escalation and Expansion Cohorts) should be performed every 7-8 days during longer infusions (Adverse events, Concomitant medications, Vital signs, Symptom driven physical exam, Hematology, Clinical chemistry, Coagulation, Urinalysis, and Plasma for PK assessment). A complete blood count (CBC with differential) should be obtained approximately half way between the weekly assessment at the study center or local laboratory.

Patients may have their dose increased to the next dose level at the next cycle if any cycle of TK216 is

well-tolerated with no clinically significant toxicity greater than Grade 2 attributed to TK216. If TK216 treatment has been well tolerated in Cycle 1 and 2, starting in Cycle 3 the duration of the TK216 infusion may be increased, in consultation with the Sponsor.

Intra-patient dose increases will be permitted during the schedule escalation segment of this trial. If any cycle of TK216 is well tolerated with no clinically significant toxicity greater than Grade 2 attributed to TK216, then the daily dose of TK216 may be increased to the next dose level on the next cycle upon discussion with the sponsor. No cycle should initiate:

1. Both vincristine for the first time and have a dose increase, or
2. Both vincristine for the first time and have an increase in the length of TK216 infusion, or
3. Increase the length of infusion for the first time and have a dose increase.

After the RP2D has been determined (recommended dose and schedule), an expansion cohort will be enrolled.

Table 2 Dose Limiting Toxicity – Part 2 Schedule Escalation Segment

Category	Criteria
Hematology toxicities	
 • Grade 4 neutropenia (absolute neutrophil count [ANC] < 500/mm³) lasting more than 7 days; • Grade 4 neutropenic fever: life-threatening consequences, urgent intervention indicated • Grade 4 thrombocytopenia (platelet count < 25,000/mm³) lasting more than 7 days; • Clinically significant thrombocytopenic bleeding;
Non-hematological toxicities	
 • Any ≥ Grade 3 toxicity that is not clinically tolerable; • For patients with liver metastases with elevated liver transaminases at baseline (2.5-5x ULN), DLT shall be defined as a doubling of the baseline liver transaminase value(s).
Failure to recover (except alopecia)	
 • Failure to recover to a clinically tolerable level of any toxicity attributed to TK216

Patients are eligible for DLT evaluation if they experience a DLT after receiving any amount of study drug or do not experience a DLT having taken a minimum of 85% of dose expected during the first cycle. Patients who do not fulfill these requirements and those who discontinue study participation prior to completing the first cycle will be replaced.

The RP2D may be determined by the MTD or optimal target inhibition with an acceptable safety profile.

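### Section 2.3 gives one trigger in Part 2 two different actions: the rule sentence escalates the dose, while the decision algorithm keeps the dose and lengthens the infusion

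*Combined protocol and SAP*

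**What the plan says.** Section 2.3 sets out a 3+3 scheme for Part 2. The starting point is fixed: "The starting daily dose level in the schedule escalation segment will be the MTD determined in the Part 1 dose escalation segment". The first cohort is infused for 10 days.

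The general rule for a tolerated cohort is that when "0 of 3, or 1 of 6 patients in a cohort experience first cycle DLT, the dose will be escalated in the subsequent cohort". Apart from one qualifier on DLT, this is the sentence that section 2.2 uses for Part 1.

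Two bullets, introduced as an illustration, then work the rule through:

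- After 0 of 3 or 1 of 6 DLTs, "the second schedule escalation cohort will receive TK216 by continuous IV infusion at the same dose for 14 days".
- Where at least two patients have a DLT, "the second schedule escalation cohort will receive TK216 by continuous IV infusion at the next lower dose for 10 days". This bullet words its condition as follows: "If 2 or more patients in the first dose escalation experience first cycle DLT".

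The section goes on: "The same decision algorithm will be used to select the dose and schedule for the third and subsequent schedule escalation cohorts". It also states: "The selection of dose and schedule for subsequent cohorts will be made by the Investigators and Sponsor", after review of the previous cohort's first-cycle results.

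**The concern.** The rule sentence and the first bullet share a trigger but prescribe different actions. A cohort cannot have its daily dose raised and also stay at the same daily dose.

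This sentence is part of the rule that assigns each Part 2 cohort its regimen, and section 1.2 makes the DLTs, MTD and RP2D the primary objective of that part. Someone following the rule sentence alone would raise the daily dose above the Part 1 MTD. Someone following the bullets would hold the dose and extend the infusion. The text also leaves it unclear, afterwards, which rule a cohort should be judged against.

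**Working it through.** **1. The plan's own figure for this trigger.** Section 9.3 tabulates the probability of escalation. Under the 3+3 rule, escalation follows 0/3 DLTs, or 1/3 followed by 0/3. With true DLT probability p:

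P(escalate) = (1−p)³ + 3p(1−p)² × (1−p)³

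For example, at p = 0.3: 0.343 + 0.441 × 0.343 = 0.4943.

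| p | Section 9.3 | Recomputed |
|---|---|---|
| 0.05 | 0.97 | 0.9734 |
| 0.1 | 0.91 | 0.9061 |
| 0.2 | 0.71 | 0.7086 |
| 0.3 | 0.49 | 0.4943 |
| 0.4 | 0.31 | 0.3093 |
| 0.5 | 0.17 | 0.1719 |
| 0.6 | 0.08 | 0.0824 |
| 0.7 | 0.03 | 0.0321 |

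All eight entries reproduce. The formula depends only on the trigger, so the table is the same whether escalation means a higher dose or a longer infusion. The problem lies in the action, not in the trigger.

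**2. What dose means in section 2.3.**

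- The starting point is expressed as a daily dose level: "The starting daily dose level in the schedule escalation segment will be the MTD determined in the Part 1 dose escalation segment".
- The first bullet goes from 10 to 14 days and calls the dose the same. With daily dose D, the cycle total rises from 10D to 14D, so the quantity held constant is the daily dose.
- The second bullet names dose and duration separately: "the second schedule escalation cohort will receive TK216 by continuous IV infusion at the next lower dose for 10 days".
- The list of combinations that may not begin in one patient's cycle includes: "Increase the length of infusion for the first time and have a dose increase". A longer infusion and a higher dose are treated there as different events.

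On that usage, the rule sentence tells the reader to raise the daily dose.

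**3. Where the literal reading leads.** Part 2 starts at the Part 1 MTD. Section 2.2 defines the MTD as a level with 0/6 or 1/6 first-cycle DLTs, where the next higher level had at least 2/3 or 2/6. If Part 2 uses the same dose ladder as Part 1 (an assumption, since Part 2 states no steps of its own), a clean first cohort would be followed by one at the level that failed in Part 1 on a 7-day infusion.

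That failure was judged by Table 1, which is stricter than Table 2. For instance, Grade 4 thrombocytopenia counts at any duration in Table 1, but only beyond 7 days in Table 2. The Part 1 result therefore gives no DLT rate for Part 2.

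**4. Side by side, after 0/3 or 1/6 in the first Part 2 cohort (D for 10 days).**

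| Source in section 2.3 | Daily dose | Duration |
|---|---|---|
| Rule sentence, read literally | Next level above D | Not stated |
| First bullet | D | 14 days |

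**The case against.** The strongest reply is that the section answers the question itself. Its stated purpose is to test longer infusions. The bullets cover the second cohort, and the algorithm sentence covers every later one, so specific text exists for each cohort the general sentence could reach. The Investigators and Sponsor choose each regimen, and the sponsor assigns the dose level at registration. Wording elsewhere is loose: section 1.2 calls Part 2 a dose escalation segment in its secondary objectives, both bullets use that label for the first schedule cohort, and section 2.2 lets within-patient dose escalation in Part 1 take the form of a longer infusion. Section 9 groups the Part 1 and 2 summaries by initially assigned dose and duration, so the regimens given will be visible in any case.

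Most of this stands, and it limits the risk. It does not reconcile the two sentences: the rule is mandatory in form, the bullets are labelled an illustration, and the looser use in section 2.2 concerns individual patients in Part 1.

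A reader might infer more than the documents support:

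- *Cohorts would be dosed above the MTD.* The algorithm and the selection step point the other way, and nothing shows that it happened. Nor is a higher dose foreign to Part 2, since section 2.3 allows further testing to define a higher MTD with prophylaxis, as well as within-patient dose increases.
- *Patients would return to a failed regimen.* If D for 10 days fails and the lower dose for 10 days is clean, the literal sentence leads back to D. That concerns the third cohort, which the algorithm sentence expressly governs, and the algorithm gives the lower dose for longer.
- *A stated multiple of exposure.* Part 2 gives no dose step and the rule sentence gives no duration, so any multiple would rest on borrowed values.

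**Conclusion.** The inconsistency is real and sits in an operative cohort-assignment rule, but its practical weight is modest. As written, the rule sentence names the wrong action for a schedule escalation. The intended action, a longer infusion at the same daily dose, is fairly clear from the rest of the section.

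The conclusion rests on reading dose as daily dose, which section 2.3 supports. The statement about the next higher level also needs an MTD established as section 2.2 defines it and the same dose ladder in Part 2. No sample size, power or escalation probability changes, and no excess exposure or DLT rate can be quantified. The correction is worth making because it is specific, bears on safety and costs almost nothing.

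**What to change.** In the rule sentence, replace the clause on escalating the dose with: *the schedule will be escalated in the subsequent cohort (longer infusion at the same daily dose) per the decision algorithm below, subject to selection by the Investigators and Sponsor*. The closing words preserve the discretion the section already grants, so dosing above the Part 1 MTD remains the sponsor's decision.

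In both bullets, change the label for the first cohort to *first schedule escalation cohort*.

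Section 2 lists Part 2 as Cohorts 7-9, and section 4.2.4 already gives a Cohort 11 regimen as of version 7.0, so Part 2 may be past assignment, although the documents do not say so. If it is, note in the study report which rule was applied to Cohorts 7-9.

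The cost is one replaced clause, two corrected labels and possibly one note. The 3+3 trigger, the sample size and the procedures stay as they are.

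### Part 2 lets a patient in a stepped-down cohort rise, from Cycle 2, to the dose and duration at which the previous cohort had two or more first-cycle DLTs

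*Combined protocol and SAP*

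**What the plan says.** All of the following is in section 2.3 of the combined protocol and SAP, except the last item.

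- **Cohort rule.** Enrolment follows a 3+3 scheme. When 2 of 3 patients have a first-cycle DLT, "accrual to the cohort will cease, and the subsequent cohort will receive TK216 at the next lower dose". The illustration for two or more DLTs in the first, 10-day cohort is that "the second schedule escalation cohort will receive TK216 by continuous IV infusion at the next lower dose for 10 days". The section adds: "The same decision algorithm will be used to select the dose and schedule for the third and subsequent schedule escalation cohorts".
- **Individual dose increase, stated twice.** The first statement reads "Patients may have their dose increased to the next dose level at the next cycle if any cycle of TK216 is" tolerated without TK216-attributed toxicity of clinical importance beyond Grade 2. The second applies the same test and adds the sponsor: "then the daily dose of TK216 may be increased to the next dose level on the next cycle upon discussion with the sponsor".
- **Individual lengthening, also stated twice.** If Cycles 1 and 2 went well, "starting in Cycle 3 the duration of the TK216 infusion may be increased (e.g. from 14 to 17 or 14 to 21 days". The restatement adds consultation with the sponsor.
- **Barred combinations.** Three pairs of changes may not start in the same cycle. Two involve first use of vincristine. The third is "Increase the length of infusion for the first time and have a dose increase".
- **Part 1 (section 2.2).** An individual increase needs two completed cycles at the assigned dose, and for a higher dose level the next cohort up must have come through Cycle 1 well.

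**The concern.** The cohort rule and the individual rule in Part 2 do not refer to each other. The cohort rule lowers the dose for new patients once a regimen has produced two or more first-cycle DLTs. The individual rule looks only at the patient's own last cycle, and one level up from a stepped-down cohort is the level that was just left.

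What is at stake is the safety of individual patients. Those in the stepped-down cohort were assigned the lower dose because of the earlier DLTs, and the written rule then allows them back to that regimen one cycle later. DLTs count only in the first cycle, so toxicity after a Cycle 2 increase would not enter the 3+3 decision. Part 1 contains a cohort condition for exactly this kind of dose increase, and the documents give no reason for leaving it out of Part 2.

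**Working it through.** **1. The path under the written rules.** Let D be a dose level and D−1 the level below it, on the same ladder going up and down.

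| Step | Regimen | Rule that leads there |
|---|---|---|
| Cohort A | D for 10 days; 2 or more first-cycle DLTs | 3+3 stop |
| Cohort B, Cycle 1 | D−1 for 10 days | Step-down, same duration (the section's own illustration) |
| Cohort B patient, Cycle 2 | D for 10 days | Individual increase after one tolerated cycle |

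The last row equals the first in dose and duration.

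**2. Does anything in the text block it?**

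- The patient's own tolerance: met by assumption at D−1. It does not test D.
- The Day 1 criteria in section 2.3 (counts, hemoglobin, recovery of other toxicity): these test the patient's recovery, not the cohort result.
- The three barred combinations: each needs two changes in one cycle. A dose increase alone is not barred.
- Sponsor discussion: present in one of the two statements of the dose rule, with no criterion.
- Section 2.6.1 (hold, resume, reduce): applies once toxicity has occurred.

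None bars D for 10 days in Cycle 2. Part 1's condition would, because the cohort at the next level up had not tolerated Cycle 1.

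**3. A longer path.** The Cohort B patient could instead go to 14 days at D−1 in Cycle 3 and to D for 14 days in Cycle 4, since only making both changes together is barred. This exceeds the stopped regimen in duration. It needs three tolerated cycles, the third already at 14 days. On the fuller wording of each rule, the sponsor is involved at both steps.

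**4. How likely is the step-down branch?** The input is the section 9.3 table. With true DLT probability p, a cohort escalates after 0 of 3, or after 1 of 3 followed by 0 of 3:

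P(escalate) = (1−p)³ + 3p(1−p)² × (1−p)³

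At p = 0.3: 0.343 + 0.441 × 0.343 = 0.494; the plan gives 0.49.

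| p | Computed P(escalate) | Plan's table | 1 − plan's table |
|---|---|---|---|
| 0.05 | 0.973 | 0.97 | 0.03 |
| 0.1 | 0.906 | 0.91 | 0.09 |
| 0.2 | 0.709 | 0.71 | 0.29 |
| 0.3 | 0.494 | 0.49 | 0.51 |
| 0.4 | 0.309 | 0.31 | 0.69 |
| 0.5 | 0.172 | 0.17 | 0.83 |
| 0.6 | 0.082 | 0.08 | 0.92 |
| 0.7 | 0.032 | 0.03 | 0.97 |

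The plan's table reproduces to its two decimals. Under this rule a cohort fails to escalate exactly when it has two or more DLTs, so the last column is the chance of the step-down branch. It is not the chance that a patient is returned to the stopped regimen, which also needs a tolerated cycle and a decision to increase. The documents give neither the true DLT probability nor those two quantities.

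**The case against.** The strongest reply is that the sponsor already holds the cohort result. Section 2.3 has the investigators and sponsor choose each new cohort's regimen after reviewing the previous cohort's first cycle. A stepped-down cohort exists because they saw the DLTs, and the sponsor discusses individual increases. The shorter statement of the dose rule can fairly be read together with the fuller one. A reader might infer that patients could be raised with no outside check; the text does not support that. What stands is that the discussion has no criterion linking it to cohort DLTs.

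Second, the setting differs from an unselected first cycle. The patient has tolerated D−1, the infusion can be held, section 2.6.1 gives hold and reduce rules, and growth factor is allowed after the first cycle. This lowers the risk. But the hold rules respond to toxicity; they do not prevent the increase. Part 1 patients must also have tolerated their dose, and Part 1 still asks for a tolerated cohort at the next level.

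Third, a 3+3 stop ends accrual and does not outlaw a regimen. Section 2.3 itself allows up to 12 more patients per dose level "to define a higher MTD and RP2D while using Cycle 1 primary supportive care prophylaxis", and patients in the stopped cohort may continue at D if they meet the Day 1 criteria. This is right. A reader might infer that the plan breaks its own stopping rule; it does not.

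Fourth, Part 1 is an imperfect model, because it lets the investigator move a patient from 7 to 14 days, which its cohorts did not test. That limits the comparison to the dose condition.

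Finally, Part 2 may be largely complete, given that Part 4 is described. The documents do not state its status, and section 2.3 is current text.

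**Conclusion.** The gap is real and narrow. Part 2's individual-increase rule carries no condition on cohort results, so a patient in a stepped-down cohort may in Cycle 2 receive the dose and duration at which the previous cohort had two or more first-cycle DLTs. The existing controls lower the risk but do not bar that regimen.

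This rests on the section's own illustration (one level lower, same 10 days), on the next level up being the one just left, and on a decision to use a permission that is optional.

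Its size in patients cannot be derived. A reader might take the 3% to 97% range as the risk to a patient; it describes only whether a cohort fails to escalate, across the true DLT probabilities in the plan's table. Nor do the documents show that any cohort was stepped down or any patient raised in this way. The point concerns what the rule permits, and the change is a cheap safety improvement.

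**What to change.** Add one sentence to section 2.3:

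*An individual patient may not be increased, by dose or by infusion duration, to a regimen with a daily dose and infusion duration both equal to or greater than those at which a Part 2 cohort had 2 or more first-cycle DLTs (Table 2), unless a later cohort has cleared that regimen (for example with prophylaxis under section 2.3).*

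State alongside it that patients already on such a regimen may continue it under the Day 1 criteria.

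This is narrower than the Part 1 condition: it closes regimens that met the stop, and everything at or above them in both dimensions, but leaves untested regimens to the existing discussion with the sponsor. It needs no new data, visits or patients. The downside is fewer individual increases, including for some patients who might have tolerated them. Patients doing well in the cohort that met the stop could stay on their regimen but could not be raised further, unless a later cohort clears the higher regimen.

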Hematology toxicities	
 Grade 4 neutropenia (absolute neutrophil count [ANC] < 500/mm³) lasting >7 days; Grade 4 anemia; Febrile neutropenia (ANC <1000/mm³ with a single temperature of > 38.3 °C or a sustained temperature of ≥ 38 °C for more than one hour); Grade ≥ 3 neutropenic infection (i.e., infection documented clinically or microbiologically with grade ≥ 3 neutropenia); Grade 4 thrombocytopenia (platelet count < 25,000/mm³); Grade 3 thrombocytopenia (platelet count < 50,000-25,000/mm³) lasting >7 days or associated with clinically significant bleeding.
Gastrointestinal toxicities	
 All ≥ Grade 4 vomiting or diarrhea; Grade 3 nausea or vomiting despite optimal antiemetic therapy that fails to recover to at least Grade 2 within 72 hours; Grade 3 diarrhea despite optimal management of the event that fails to recover to at least Grade 2 within 72 hours.
CNS toxicities	
 Grade ≥ 3
Other non-hematological toxicities	
 Grade ≥ 3; Grade 2 increase in AST/ALT in combination with a grade 2 increase in bilirubin; For patients with liver metastases with elevated liver transaminases at baseline (2.5-5x ULN), DLT shall be defined as a doubling of the baseline liver transaminase value(s); Toxicity of any grade that interrupts the first seven day infusion for ≥24 hours.
Failure to recover (except alopecia)	
 Failure to recover to Grade ≤ 2 toxicity or to baseline values after delaying the initiation of next cycle by a maximum of 21 days

Patients are eligible for DLT evaluation if they experience a DLT after receiving any amount of study drug or do not experience a DLT having taken a minimum of 85% of dose expected during the first cycle. Patients who do not fulfill these requirements and those who discontinue study participation prior to completing the first cycle will be replaced.

The MTD is the dose level at which 0 of 6 or 1 of 6 patients experience first-cycle DLT, and at least 2 of 3 or 2 of 6 patients experience first-cycle DLT at the next higher dose level. Effectively, the MTD is the highest dose associated with first-cycle DLT in < 33% of patients.

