2.6.1 Dose modifications

2.6.1.1 Dose reductions (Parts 1-3)

Dose or schedule reduction for patients may be warranted after Cycle 1 as a consequence of drug-related toxicities. Dose reduction will be documented in the CRF along with reason for reduction. The decision to reduce the dose will be made by the Investigator, who may consult with the Sponsor if indicated.

At a starting dose level of 18 mg/m²/day, no dose reduction is anticipated for patients in the first cohort. If unacceptable toxicity occurs in a patient, then that patient will be instructed to stop treatment.

Patients with toxicities that are manageable with supportive therapy may not require dose reductions (e.g., nausea/vomiting may be treated with antiemetics). Patients with toxicities up to Grade 3 that are clinically tolerable in the Investigator's opinion may not require dose reductions (e.g. severe diarrhea of short duration).

For adverse events not specified below, doses may be reduced or held at the discretion of the investigator for the patient's safety. The sponsor should be made aware of such reductions.

Suggested dose modifications based on type of AE or laboratory findings:

Grade 4 neutropenia or clinically intolerable Grade 3 neutropenia:

- First occurrence- hold TK216 until ANC $\geq 1,000/\text{mm}^3$, then resume TK216 at same dose and schedule.
- Second or subsequent occurrence- hold TK216 until ANC $\geq 1,000/\text{mm}^3$, then reduce TK216 daily dose to one dose level lower than the current dose.

Patients experiencing \geq Grade 2 neutropenia may receive G-CSF or other myeloid growth factors after the first cycle or as defined in the dose and schedule escalation plan.

Grade 4 thrombocytopenia or any clinically significant thrombocytopenic bleeding:

- First occurrence- hold TK216 until platelets $\geq 50,000/\text{mm}^3$, then resume TK216 at same dose and schedule.
- Second or subsequent occurrence- hold TK216 until platelets $\geq 50,000/\text{mm}^3$, then reduce TK216 dose to one daily dose level lower than the current dose.
- Use of platelet growth factors or platelet transfusions is permissible.

Hemoglobin ≤ 8.0 gm/dL

- Any occurrence- hold TK216 until hemoglobin ≥ 8.0 gm/dL, then resume TK216 at same dose. Blood transfusions are permitted.

Grade 3 or greater non-hematologic toxicity (unless clearly and incontrovertibly unrelated to TK216):

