4.2.2.2 Day 2, Cycle 1 Assessments, Continuation of Hospitalization (Cohorts 1, 2, 3)

On Day 2 of Cycle 1 of dose escalation Cohorts 1, 2 and 3, the procedures listed below will be performed:

- a 12-lead ECG will be done on Day 2 between hours 14 and 16 hours after the start of the infusion on Day 1 (to coincide with the plasma PK samples done at the same time points).
- plasma PK samples at 14 hours, 15 hours and 16 hours after starting the infusion on Day 1;
- suspend infusion 16 hours after starting on Day 1 (immediately after drawing 16 hour PK sample), in the morning of Day 2;
- plasma PK samples at 0.5, 1, 2, 4 and 8 hours after discontinuing the infusion;
- restart infusion 8 hours later, in the late afternoon; infusion will then be continuous until Day 8;
- clinical laboratory tests (hematology, clinical chemistries, coagulation, urinalysis);
- vital signs;
- symptom-driven physical examination;
- concomitant medication assessment;
- adverse event assessment.

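### In Part 2, a patient whose first infusion is cut below 85% by TK216 toxicity short of a Table 2 DLT is replaced and leaves the escalation count

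*Combined protocol and SAP*

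**What the plan says.** Section 2.3 sets up Part 2 to find out how well longer infusions are tolerated. Escalation rests on first-cycle DLTs: 0 of 3 or 1 of 6 permits it. A patient with a DLT is evaluable after any amount of drug. Patients without one are evaluable only if they "do not experience a DLT having taken a minimum of 85% of dose expected during the first cycle". The next sentence reads: "Patients who do not fulfill these requirements and those who discontinue study participation prior to completing the first cycle will be replaced". Neither sentence distinguishes shortfalls by cause.

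Table 2 counts cytopenias as DLTs only when they last: "Grade 4 neutropenia (absolute neutrophil count [ANC] < 500/mm³) lasting more than 7 days" and "Grade 4 thrombocytopenia (platelet count < 25,000/mm³) lasting more than 7 days". It also counts Grade 4 neutropenic fever, significant thrombocytopenic bleeding, non-hematological toxicity of Grade 3 or higher that is not clinically tolerable, a transaminase rule for patients with liver metastases, and failure to recover. It does not list anemia.

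Table 1, for Part 1, has one further item: "Toxicity of any grade that interrupts the first seven day infusion for ≥24 hours". Table 2 has no equivalent, although the evaluability wording is the same in both parts.

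Section 2.6.1.1 gives suggested modifications for Parts 1 to 3. For Grade 4 neutropenia of any duration: "First occurrence- hold TK216 until ANC" is back to at least 1,000/mm³. There are similar holds for Grade 4 thrombocytopenia (until platelets reach 50,000/mm³), for low hemoglobin, and for non-hematologic toxicity of Grade 3 or higher.

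**The concern.** Being unable to finish a longer infusion because of the drug is the outcome that Part 2 sets out to measure. If such a patient has no Table 2 DLT, the evaluability rule takes the patient out of the cohort and puts another in. Replacement then depends on the outcome itself. The escalation rule sees the DLT rate among patients who either had a DLT or received nearly all of the drug, and it never sees the toxicity-driven shortfalls. The Part 2 result feeds the RP2D, which Part 3 then uses.

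**Working it through.** **1. The plan's own figure.** With true event probability p, the chance of escalating (0 of 3, or 1 of 3 followed by 0 of 3) is

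P(p) = (1−p)³ + 3p(1−p)⁵.

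At p = 0.20 this is 0.512 + 0.197 = 0.709. The formula reproduces all eight values in Section 9.3 (0.97, 0.91, 0.71, 0.49, 0.31, 0.17, 0.08, 0.03).

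**2. How much lost infusion makes a patient non-evaluable.** The threshold is 15% of the planned length.

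- Part 1, 7 days: 0.15 × 168 h = 25.2 h. A single toxicity interruption of 24 h is already a DLT under Table 1, so the gap is largely closed.
- Part 2, 10 days: 0.15 × 240 h = 36 h.
- Part 2, 14 days: 0.15 × 336 h = 50.4 h.

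**3. Whether the plan's own rules lead there.** Grade 4 neutropenia is ANC below 500, but the hold lasts until ANC is at least 1,000. Grade 4 thrombocytopenia is below 25,000, but the hold lasts until 50,000. A hold can therefore outlast the Grade 4 period that Table 2 times. In the Part 2 visit text (Section 6.3.5), the first on-treatment safety laboratory draw is at Day 8 ± 1. A hold that starts on Day 7 to 9 and runs to the planned end of a 10-day infusion leaves 6 to 8 days delivered, or 60% to 80%. That is below 85% and need not be a DLT. This step assumes that held days are not made up.

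**4. Effect on escalation.** Let t be the probability of a Table 2 DLT and r the probability of a toxicity-driven shortfall without a DLT. The two are mutually exclusive, and both values are assumed because the documents give neither. Under replacement, the decision sees t/(1−r). If shortfalls count as events, it sees t + r. If these patients stay in the cohort as DLT-free, it sees t. With t = 0.10:

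| r | t/(1−r) | P, replaced | t + r | P, counted as events | P, kept as DLT-free |
|---|---|---|---|---|---|
| 0.05 | 0.105 | 0.90 | 0.15 | 0.81 | 0.91 |
| 0.10 | 0.111 | 0.89 | 0.20 | 0.71 | 0.91 |
| 0.20 | 0.125 | 0.86 | 0.30 | 0.49 | 0.91 |
| 0.30 | 0.143 | 0.83 | 0.40 | 0.31 | 0.91 |

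For r = 0.20, replaced: 0.875³ + 3(0.125)(0.875⁵) = 0.670 + 0.192 = 0.862. Counted: 0.343 + 0.151 = 0.494.

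At r = 0.20 with other DLT rates, replaced against counted is 0.96 against 0.60 (t = 0.05) and 0.60 against 0.31 (t = 0.20).

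The chance that filling three evaluable places involves at least one such replacement is 1 − (1−r)³: 0.14, 0.27 and 0.49 at r = 0.05, 0.10 and 0.20.

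**The case against.** Several points on the other side have force.

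- **Direction.** Measured against the protocol's own DLT definition, replacement raises the observed rate, since t/(1−r) exceeds t. The rule looks lenient only if a toxicity-driven shortfall is regarded as evidence against tolerability. This stands, and it shapes the fix: keeping these patients as DLT-free would make escalation more likely than now (last column of the table).
- **Holds.** They are suggestions, in a section that speaks of reductions after Cycle 1, and the text does not say whether missed days are made up. However, the holds are not confined to later cycles, and nothing says that the infusion is extended.
- **Visibility.** The investigators and sponsor review first-cycle results before choosing the next regimen, interruptions are recorded (Section 7.4), and every treated patient enters the safety analyses (Section 9.4). Those routes inform judgment, but the stated 0 of 3 or 1 of 6 rule still runs on DLTs alone.
- **Intent.** Table 2 is looser than Table 1 elsewhere too, so leaving out the interruption item may be deliberate. That would explain not calling it a DLT; it would not explain replacing the patient.

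A reader might infer that the rule discards exactly the patients who could not tolerate the infusion. Table 2 does not support that: intolerable non-hematological toxicity of Grade 3 or higher, prolonged Grade 4 cytopenia, significant bleeding and failure to recover are DLTs after any amount of drug. The group at risk is narrower: shorter cytopenias, low hemoglobin, and lower-grade or tolerable events that lead to a hold.

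A reader might also infer the same gap in Part 1, because Cycle 1 has a planned pause ("restart infusion 8 hours later, in the late afternoon"). That needs the expected dose to mean a full 168 h, although the pause is scheduled, and it needs clock times that the text does not give. With an assumed 17:00 start and 09:00 stop, 16 + 136 = 152 h are scheduled. The permitted loss is then 0.15 × 152 = 22.8 h, about 1 h short of the 24-hour DLT item. No material gap follows.

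**Conclusion.** The gap is real and belongs to Part 2. The 85% sentence can replace a patient whose first cycle was cut short by TK216 toxicity that Table 2 does not count, and Table 1's safeguard was not carried over. The Part 2 escalation count can therefore omit drug-related inability to complete the infusion.

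The size is not known. At an assumed DLT rate of 0.10, the difference in escalation probability runs from 0.09 (0.90 against 0.81, r = 0.05) to 0.37 (0.86 against 0.49, r = 0.20). It rests on three assumptions: the values of t and r, held days not being made up, and shortfalls being counted against tolerability. The mechanism itself follows from the text.

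**What to change.** Limit replacement in Section 2.3 to shortfalls not attributed to TK216. State that a patient below 85% because of toxicity at least possibly related to TK216 stays in the cohort and enters the escalation decision as evidence against tolerability, not as a DLT-free completer. State whether infusion days lost to a hold are made up. At each cohort review, and in the DLT table, show these patients by reason beside the DLT count.

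The Part 2 evaluability text and Table 2 must be reconciled with Table 1 and Section 2.6.1 on how toxicity-driven interruptions count. Which interruptions are DLTs is a clinical decision for the sponsor and investigators.

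The cost is protocol wording and one extra column in the cohort review. Some cohorts may escalate more slowly.
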